6.3 HANDLING OF DERIVED VARIABLES

The baseline is considered to be the start date of the first administration of Esgliteo and the baseline value is defined as the last value measured before the first administration.

Derivation/imputation of variables will be performed as in the following.

Table 3 Derived variables

Variable	Derivation Method
Change from baseline	Post-baseline value – Baseline value
Age group	Less than 19 years 19 years or older and less than 30 years 30 years or older and less than 40 years 40 years or older and less than 50 years 50 years or older and less than 60 years 60 years or older
Duration of disease (years)	(Date of data release consent – Diagnosed date) / 365.25
Geriatric population	65 years or older, Less than 65 years
Total period of drug use(days)	End date of Esgliteo final administration – Start date of Esgliteo first administration+1 If [Continuing] is checked on CRF [DISPENSING OF ESLITEO] page, end date of Esgliteo final administration will be replaced with date of last safety assessment, and if date of last safety assessment is missing, it is replaced with date of last visit.
10/5mg, 25/5mg Sum of total period of drug use(days)	Sum of ((End date of Esgliteo administration - Start date of Esgliteo administration +1) per duration of visit) If [Continuing] is checked on CRF [DISPENSING OF ESLITEO] page, end date of Esgliteo final administration will be replaced with date of last safety assessment, and if date of last safety assessment is missing,

CONFIDENTIAL

STATISTICAL ANALYSIS PLAN

Variable	Derivation Method
	it is replaced with date of last visit.
Total number of administrations	Sum of (Administration frequency ^[1] ×period of drug use) per duration of visit [1] QD: Once a day, BID: Twice a day, TID: Three times a day, QID: Four times a day, PRN: Whenever necessary But, the value collected with PRN is excluded from analysis.
Average number of administrations per day	Total number of administrations / Total period of drug use
Duration of AE (Days)	AE end date – AE onset date +1 If [Continuing] is checked on CRF [ADVERSE EVENTS] page, AE end date will be replaced with date of last safety assessment, and if date of last safety assessment is missing, it is replaced with date of last visit, and will mark \geq (e.g. ≥ 15).
Onset duration of AE	AE onset date – Date of first Esglito administration
Less than 7% of HbA1c	yes: HbA1c $< 7\%$ no: HbA1c $\geq 7\%$
Decreased by at least 0.5% of HbA1c	yes: HbA1c measurements at baseline – HbA1c measurements after baseline $\geq 0.5\%$ no: HbA1c measurements at baseline – HbA1c measurements after baseline $< 0.5\%$

6.4 DEFINITION OF ANALYSIS VISIT

Analysis visits for effectiveness set are defined as follows.

If more than one visit result exists in the visit 2 analysis acceptance range, the results closer to the planned visit in protocol are considered as the visit result and the visit result(e.g. -3 days) investigated previously is included in the analysis if the absolute value of the visit day difference is the same (e.g. -3 days, +3 days).

If more than one visit result exists in the visit 3 analysis visit acceptance range, the visit result with a larger visit date interval is included in the analysis.

CONFIDENTIAL

STATISTICAL ANALYSIS PLAN

Table 4 Definition of analysis visit

Analysis visit	Period	Visit window (day)	Analysis acceptance range (day)
Baseline	1		
Visit 2	84	+83	$84 \leq \text{Visit 2-Baseline} + 1 < 168$
Visit 3	168		$168 \leq \text{Visit 3-Baseline} + 1$

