- Any changes in laboratory tests if there is any lab result which was clinically significant compared to data before Esgliteo therapy (This data is collected on the basis of medical need, i.e. independent of the NIS)
- Any adverse events noted, AESI (Adverse Event of Special interest)
- Study completion status (if necessary)

- The final effectiveness evaluation(if necessary)
- NIS physician's electronic signature for data integrity (if necessary)

9.2.3.4 Visit 3; 24 weeks from Visit 1

After 24 weeks from Visit 1, the patients will return for follow-up. The followings will be noted and recorded in the eCRF.

- Visit date
- Physical examination: body weight, blood pressure(SBP, DBP)
- Any changes of Esgliteo given
- Effectiveness endpoints: HbA1c, FPG (Within 1month prior to Visit 3)
- Renal function test: Serum creatinine, eGFR, Urine ACR if blood test result is available (The most recent data since last visit, except previously entered data)
- Concomitant anti-hyperglycemic agent including new medications taken since last visit: any changes in the concomitant medications (dose and dosing intervals)
- Concomitant medications including new medications taken since last visit: any changes in the concomitant medications (dose and dosing intervals)
- Any changes in laboratory tests if there is any lab result which was clinically significant compared to data before Esgliteo therapy (This data is collected on the basis of medical need, i.e. independent of the NIS)
- Any adverse events noted, AESI (Adverse Event of Special interest)
- Study completion status(if necessary)
- The final effectiveness evaluation
- NIS physician's electronic signature for data integrity

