9.1 PRIMARY ENDPOINT

For HbA1c, the changes from baseline to 12 and 24 weeks will be summarized using number of subjects, mean, SD, median, minimum, maximum, 5th percentile and 95th percentile, and will be compared using paired t-test.

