9.8 THE FINAL EFFECTIVENESS EVALUATION FOR LONG-TERM EFFECTIVENESS SET

For the final effectiveness evaluation, the three items ([Improved, Unchanged, Aggravated]) at the time of week 24 will be summarized for Long-term effectiveness set using number of subjects, percentage, 95% confidence intervals. In addition, if final effectiveness is evaluated as [Improved], it is classified as [Efficacy]. And If final effectiveness is evaluated as [Unchanged, Aggravated], it is classified as [Inefficacy].

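### SAP 6.4 accepts any result from day 168 onward as Visit 3 and keeps the latest one, but the tables report it as the 24-week value

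*SAP*

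**What the plan says.** Study day is counted from first dose (SAP 6.3: "The baseline is considered to be the start date of the first administration of Esgliteo"). SAP Table 4 plans Visit 2 at day 84, with a window of +83 days and an acceptance range from day 84 to below day 168. It plans Visit 3 at day 168, with an acceptance range that has a lower limit (day 168) and no upper one.

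SAP 6.4 settles multiple results differently for the two visits. At Visit 2, "the results closer to the planned visit in protocol are considered as the visit result". At Visit 3, "the visit result with a larger visit date interval is included in the analysis".

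The selected values feed rows defined by week. For HbA1c, SAP 9.1 states that "the changes from baseline to 12 and 24 weeks will be summarized". SAP 9.2(1) and 9.2(3) use the same time points for response below 7%, FPG, weight and blood pressure, and SAP 9.6 and 9.7 do so for the long-term effectiveness set.

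Protocol 9.2.3.4 times the visit from Visit 1 and gives no tolerance: "After 24 weeks from Visit 1, the patients will return for follow-up". Its one-month limit ties the HbA1c and FPG sample to the visit date. It does not tie the visit to week 24.

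Protocol 9.7.3 works differently: its descriptive changes and both HbA1c response rates are taken at the last visit.

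**The concern.** The two selection rules pull in opposite directions. Visit 2 prefers the value nearest its planned day. Visit 3 prefers the value furthest from it, in a range that never closes. A reader of the 24-week row would take it to describe patients after about 24 weeks of treatment, yet the row can mix results from very different durations, and nothing in the planned tables would show this.

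Change in HbA1c after 12 and/or 24 weeks is the primary effectiveness endpoint (Protocol 9.3.2.2.1), so the rule governs one of its two time points. It also governs the 24-week results for response below 7%, FPG, weight and blood pressure.

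**Working it through.** **Inputs.** Table 4 day limits and the two selection rules (SAP 6.4); planned start and end of data collection, 30 Oct 2021 and 30 Nov 2022 (Protocol 6, SAP Table 1); three contacts per patient (Protocol 9.3.1, SAP 4); N = 600 (SAP 2.2).

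**1. Reproduce Table 4.** 12 × 7 = 84 and 24 × 7 = 168. 84 + 83 = 167, the last day below 168. The Visit 2 window reproduces exactly and meets the start of the Visit 3 range. No corresponding figure closes Visit 3.

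**2. Meaning of the larger interval.** Every eligible Visit 3 day is on or after planned day 168. Whether the interval is counted from baseline or from the planned day, the larger one belongs to the later result.

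**3. Apply the rules to example patients.**

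| Result days | Visit 3 value under SAP 6.4 | Value nearest day 168 |
|---|---|---|
| 84, 168 | 168 (week 24.0) | 168 |
| 90, 350 | 350 (week 50.0) | 350 |
| 169, 337 | 337 (week 48.1) | 169 |
| 168, 350 | 350 (week 50.0) | 168 |
| 100, 169, 396 | 396 (week 56.6) | 169 |

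In the second row a lone late visit is labelled week 24 and nothing is discarded. In the last three rows an on-time or nearly on-time result is dropped for a later one.

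**4. Latest possible visit day.** 30 Oct 2021 to 30 Nov 2022, counting both days, gives day 397. 397 / 7 = 56.7 weeks, and 397 − 168 = 229 days past the planned day. This is a ceiling: it needs first dose on the first day of collection and a visit on the last. The HbA1c sample itself may be up to a month older than the visit. If collection instead ran to the end of the re-examination period, 30 Mar 2023 (an assumption), the ceiling would be day 517 (week 73.9).

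**5. Who could reach week 50.** Day 350 by 30 Nov 2022 needs first dose by 16 Dec 2021, that is, in the first 48 days of collection. Day 168 by the same date needs first dose by 16 Jun 2022, that is, within 230 days. If enrolment were uniform over those 230 days (an assumption), 48 / 230 = 21%, or about 125 of 600 patients, could have a value that late. This says how many could, not how many would.

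**6. Effect of the nearest-to-plan rule on numbers.** A patient contributes to the 24-week row if at least one result lies at or after day 168. Choosing the nearest instead of the latest does not alter who meets that condition, so no patient leaves the row, provided the choice is made among the recorded values of each variable.

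**The case against.** The strongest defence is that the rule carries out the protocol. Protocol 9.7.3 analyses the last visit, the endpoint wording allows 12 and/or 24 weeks, and the SAP's long-term sets are defined as 24 weeks or more. Taking the latest value from day 168 fits all of this. That stands as an explanation of the rule, but it does not justify the label. SAP 9.2(4) asks for change to the latest value, while 9.1, 9.2(1) and 9.2(3) ask for weeks 12 and 24, so the SAP itself treats these as different quantities. SAP section 11, which lists departures from the protocol, mentions only the replacement of average daily dose.

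The second defence is rarity, and it stands. Each patient has three contacts and only one is due at or after week 24. Dropping an on-time value needs an extra visit or a Visit 2 that slips badly. In the example with days 169 and 337, Visit 2 is 169 − 84 = 85 days late and Visit 3 is 337 − 168 = 169 days late. A reader might infer that on-time values will routinely be replaced by values from week 50 or later; the documents do not support that. The case of a single late visit needs no second result and is the more likely of the two.

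The third defence is limited consequence. Effectiveness is the secondary objective of a single-arm study that the protocol abstract describes as descriptive. That keeps the point moderate.

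**Conclusion.** The mismatch is real, and it is one of definition: a variable that holds the last value at or after day 168 is reported as the 24-week value, under a selection rule opposite to the SAP's own rule for Visit 2. Within the planned dates a value labelled week 24 can come from a visit as late as day 397. The number of patients affected is unknown. The conclusion rests on the acceptance range in Table 4, which is legible and open-ended; the blank window cell for Visit 3 is not relied on.

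Three further inferences are tempting but go beyond the documents.

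- Late values might be thought to come from patients with longer treatment, dose changes or added antidiabetic agents. Such changes are allowed and recorded, but nothing links them to late visits, so no direction of bias can be stated.
- SAP 9.8 says that the final effectiveness evaluation "at the time of week 24 will be summarized for Long-term effectiveness set". That is a physician's rating recorded at the end of the last visit (Protocol 9.3.2.2.3), not a choice among repeated measurements, and it is not shown to be affected.
- The +83 days of Visit 2 might be carried over to give a hard limit at 168 + 83 = day 251. That figure only makes the Visit 2 range meet Visit 3 and is no rationale for a Visit 3 tolerance. As a limit on the main analysis it would remove observed data, contrary to Protocol 9.7.5.

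**What to change.** 1. In SAP 6.4, for the 24-week rows, apply the Visit 2 rule to Visit 3: among results in range, use the one nearest planned day 168, chosen separately for each variable among its recorded values. Because the range starts at the planned day, this is the earliest result in range.
2. Report the last value at or after 24 weeks as a separate row, named as such, for the last-visit analyses (Protocol 9.7.3; SAP 9.2(2), 9.2(4) and 9.7(2)). SAP 9.2(2) and 9.7(2) name both weeks 12 and 24 and the last visit, so state there which row answers which.
3. Show the distribution of Visit 3 study days: median, range and 5th and 95th percentiles.
4. Leave the main analysis without a hard upper limit. If a limit is wanted, use it in a sensitivity analysis only, justify the figure, and give the number of values beyond it.

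The cost is one changed sentence, a small programming change and one more row or table. The SAP file is dated 19 April 2023, after the planned end of data collection on 30 Nov 2022, so the change and its reason should be documented, as SAP section 1 already requires for departures from the plan. Recorded visit dates should also show how many patients are affected.

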6.5 HOW TO HANDLE DATA ERRORS AFTER DB LOCK

If an ‘Error List After DB Lock’ (supporting document 0314 D) document according to ‘SOP 0314’ Database Lock is created after DB lock, the related content is not reflected in the analysis and written in the comments.

7. SUBJECT INFORMATION**7.1 STUDY PERIOD AND NUMBER OF SUBJECTS**

The study year and study period will be presented. The number of subjects whose CRF was retrieved, safety set, effectiveness set, long-term safety set, long-term effectiveness set by year of the study will be presented.

7.2 POST-MARKET SURVEILLANCE TABLES

The study sites and study Principal Investigator will be presented. The number of subjects whose CRF was retrieved, safety set, effectiveness set, long-term safety set, long-term effectiveness set by year of the study will be presented.

7.3 SUBJECT CHARACTERISTICS

Subject characteristics will be performed on safety set.

7.3.1 Demographics

For the following variables, the continuous variables will be summarized using number of subjects, mean, SD, median, minimum, maximum, 5th percentile and 95th percentile, and the categorical variables will be summarized using number of subjects and percentages.

CONFIDENTIAL

STATISTICAL ANALYSIS PLAN

- Continuous variable: Age(Years), Height(cm), Weight(kg)
- Categorical variable: Age group, Gender, Smoking status

7.3.2 Disease information

For the following variables, the continuous variables will be summarized using number of subjects, mean, SD, median, minimum, maximum, 5th percentile and 95th percentile, and the categorical variables will be summarized using number of subjects and percentages.

- Continuous variable: Duration of disease (years)
- Categorical variable: Family history of T2DM, Previous allergy, Diabetes mellitus complications (Retinopathy, Neuropathy, Nephropathy, Vasculopathy, Other), Medical history, Comorbidities, Prior/Concomitant medication, Other anti-diabetic agent

7.3.3 Subjects of special investigation

The following variables will be summarized using number of subjects and percentages.

[figure not shown]
- Geriatric population (65 years or more, Less than 65 years)
- Pregnant women (Yes, No, Not applicable)
- Renal impairment (Yes, No)
- Hepatic impairment (Yes, No)
- Long-term use (24 weeks or more)

7.3.4 Medical history and comorbidities

Previous medical history is defined as those that are blanked for the question “Ongoing” under [Medical History] page of the CRF, and comorbidities are defined as those that are checked “1” for the same question.

Medical history and comorbidities will be summarized with number of subjects, percentages and number of cases. Medical history and comorbidities will be coded with Medical Dictionary for Regulatory Activities (MedDRA) latest major version and will be summarized with system organ class (SOC) and preferred term (PT) using number of subjects, percentages and number of cases.

CONFIDENTIAL

STATISTICAL ANALYSIS PLAN

7.3.5 Prior and concomitant medication

Prior medication is defined as any medication that the subjects took before the first dose of Esgliteo. Concomitant medication is defined as any medication that the subjects took on or after the first dose of Esgliteo.

Prior medication is any medication that can be classified into the following category.

- Medication start date < Start date of first Esgliteo administration

Concomitant medication is any medication that can be classified into the following category.

- Medication start date \geq Start date of first Esgliteo administration

Table 5 Examples of categorization

Medication start date	Medication end date	Date of first Esgliteo administration	Prior medication	Concomitant medication
2020-01-01	2020-01-14	2020-01-15	Y	
2020-01-01	2020-01-15	2020-01-15	Y	
2020-01-01	2020-01-20	2020-01-15	Y	
2020-01-01	Ongoing	2020-01-15	Y	
2020-01-15	2020-01-15	2020-01-15		Y
2020-01-15	2020-01-20	2020-01-15		Y
2020-01-15	Ongoing	2020-01-15		Y
2020-01-20	2020-01-25	2020-01-15		Y
2020-01-20	Ongoing	2020-01-15		Y

If there is a missing date, Prior/concomitant medication is classified by processing according to [6.2 Handling of Missing Dates].

Prior and concomitant medications will be summarized with number of subjects, percentages and number of cases. Prior and concomitant medications will be coded using the World Health Organization Anatomical Therapeutic Chemical index (WHO ATC index) latest version and

CONFIDENTIAL

STATISTICAL ANALYSIS PLAN

will be summarized with Level 1 (anatomical main group) and Level 5 (chemical substance) using number of subjects, percentages and number of cases. However, if level 5 is 'Combinations', 'Various' or 'various combinations', then level 4 will be used instead. (If level 5 doesn't exist then a higher level will be used.) The frequency is counted as one person in each classification (Subjects investigated with prior and concomitant medication, level 1 and level 5) even if one subject has multiple prior/concomitant medications.

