7.3.6 Other anti-diabetic agent

Subjects who used other anti-diabetic agent during the study will be summarized with number of subjects, percentages and number of cases and will be coded using the World Health Organization Anatomical Therapeutic Chemical index (WHO ATC index) latest version and will be summarized with Level 1 (anatomical main group) and Level 5 (chemical substance) using number of subjects, percentages and number of cases. However, if level 5 is 'Combinations', 'Various' or 'various combinations', then level 4 will be used instead. (If level 5 doesn't exist then a higher level will be used.) The frequency is counted as one person in each classification even if one subject use multiple other anti-diabetic agent.

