8.3 SAFETY ANALYSES BY FACTORS

8.3.1 Univariate analysis

The following categorical variables will be summarized using number of subjects, the number of subjects and proportion of the number of subjects with AE and 95% confidence interval. AE Occurrence will be analyzed using Pearson's chi-square test or Fisher's exact test to determine if statistically significant differences exist. (However, if [Diabetes mellitus complications] responds with [Not applicable], [Pregnancy] responds with [Not applicable], [Height] responds with [Not done], it is excluded from Pearson's chi-square test or Fisher's exact test.)

- Gender (Male, Female)
- Smoking status (Never smoked, Ex-smoked, Currently smokes)
- Family history of T2DM (Yes, No)
- Previous allergy (Yes, No)
- Diabetes mellitus complications (Retinopathy, Neuropathy, Nephropathy, Vasculopathy, Other) (Yes, No, Not applicable)
- Medical history (Yes, No)
- Comorbidities (Yes, No)
- Prior medication (Yes, No)
- Concomitant medication (Yes, No)
- Other anti-diabetic agent (Yes, No)

For the following continuous variables AE Occurrence will be summarized using odds ratio and 95% confidence interval for an increase or decrease per defined unit of the variable based on using simple logistic regression.

- Age (years)
- Height (cm)
- Weight (kg)

CONFIDENTIAL

STATISTICAL ANALYSIS PLAN

- Duration of disease (years)
- Total period of drug use (days)
- Total number of administrations
- Average number of administration per day

Subjects of special investigation will be summarized using number of subjects, number of subjects with AE, proportion of subjects with AE and 95% confidence interval. AE Occurrence will be analyzed by using Pearson's chi-square test or Fisher's exact test to confirm statistically significant differences.

- Geriatric population (65 years or more, Less than 65 years)
- Pregnant women (Yes, No, Not applicable)
- Renal impairment (Yes, No)
- Hepatic impairment (Yes, No)
- Long term use (24 weeks or more)

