10.5 DETAILS OF SERIOUS UNEXPECTED AEs

The details of Serious Unexpected AEs collected from use result surveillance, special study (Pharmacoepidemiology study, etc.), clinical trials and Spontaneous reporting will be presented in a listing.

11. Changes to the planned analysis method

In the 9.7.1 demographic analysis item of Protocol (version 4.0), it is described that the administration status of this drug (average daily dose) is analyzed, but since Esglito is a composite, the average number of administrations per day will be analyzed.

[figure not shown]
12. SAS program code

The following SAS program codes will be used.

Table 6 SAS program code

Analysis method	SAS program code
Pearson's chi-square test or	PROC FREQ DATA=dataset;
Fisher's exact test	TABLE ae*factor/CHISQ EXACT; RUN;
Paired t-test	PROC UNIVARIATE DATA=dataset; VAR diff;

CONFIDENTIAL

STATISTICAL ANALYSIS PLAN

Analysis method	SAS program code
	RUN;
t-test	PROC TTEST DATA=dataset; CLASS factor; VAR chg; RUN;
ANOVA	PROC MIXED DATA=dataset; CLASS treatment; MODEL variable=treatment; LSMEANS treatment / PDIFF CL; RUN;
Simple logistic regression	PROC LOGISTIC DATA=dataset; CLASS factor; MODEL ae=factor; RUN;
Multiple logistic regression	PROC LOGISTIC DATA=dataset; CLASS factor1 factor2 factor3; MODEL ae= factor1 factor2 factor3 factor4; RUN;

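### SAP 7.3.5 classes medicines still in use at the first Esgliteo dose as prior only, against its own definition of concomitant medication

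*SAP*

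**What the plan says.** SAP 7.3.5 gives two definitions in words. For the first category: "Prior medication is defined as any medication that the subjects took before the first dose of Esgliteo". For the second: "Concomitant medication is defined as any medication that the subjects took on or after the first dose of Esgliteo". Nothing in these sentences makes the categories exclusive; a medicine begun earlier and continued past the first dose meets both.

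The section then gives an operational rule for each. Prior is "Medication start date < Start date of first Esgliteo administration" and concomitant is "Medication start date \geq Start date of first Esgliteo administration". Neither uses the end date or the ongoing tick. Table 5 illustrates the rule with nine medicines, and none is marked in both columns. Missing dates are first completed under SAP 6.2, where Table 2 sets an unknown start day to 01.

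The flag feeds Table B7 and is a Yes/No factor in SAP 8.3.1 (AE occurrence), 9.2 item 4 (HbA1c change), 9.4 (final effectiveness) and 9.7 item 4 (HbA1c change, long-term set).

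Neighbouring text uses the broad meaning:
- SAP 7.3.6 counts other anti-diabetic agents by use: "Subjects who used other anti-diabetic agent during the study will be summarized". It states no start-date rule.
- Protocol 9.1.3 includes therapies begun in the month before Esgliteo among the concomitant medication to be recorded.
- Protocol 9.2.3.2 records medicines taken in the month before baseline under the concomitant heading.

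SAP section 11 declares one change from the protocol, on daily dose ("the average number of administrations per day will be analyzed"), and nothing on this point.

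**The concern.** The definition and the rule give different answers for the commonest kind of co-medication: a long-term medicine started before Esgliteo and continued alongside it. Because the rule and the worked examples agree with each other, a programmer will implement them.

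Two outputs then mislead. Table B7 shows only medicines begun on or after the first dose. The Yes/No factor compares patients who started something new with everyone else, and that second group includes patients taking only stable co-medication. A reader of C16, D5, D7 or D15 would take it as users against non-users. The Yes group is also enriched with patients given a drug to treat an adverse event, which matters most in C16 because safety is the primary objective.

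The reach is limited. Overall AE rates, the SOC/PT tables and the overall HbA1c change do not use the flag, and anti-diabetic agents have their own Table B8.

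**Working it through.** **1. Table 5 under each reading.** The first dose is 2020-01-15 in every row. The definition in words is read as: concomitant if the end date is on or after the first dose, or the medicine is ongoing.

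| Row | Start | End | Table 5 | Start-date rule | Definition in words |
|---|---|---|---|---|---|
| 1 | 01-01 | 01-14 | Prior | Prior | Prior |
| 2 | 01-01 | 01-15 | Prior | Prior | Prior and concomitant |
| 3 | 01-01 | 01-20 | Prior | Prior | Prior and concomitant |
| 4 | 01-01 | Ongoing | Prior | Prior | Prior and concomitant |
| 5–9 | 01-15 or 01-20 | on/after 01-15 or ongoing | Concomitant | Concomitant | Concomitant |

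The rule reproduces 9 of 9 rows. The definition reproduces 6 of 9 and differs exactly in rows 2, 3 and 4. The Prior mark there is right under both readings; the Concomitant mark is what is missing.

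**2. Imputed dates.** Suppose the first dose is 2022-03-10 and a medicine is recorded from 2022-03-UK to 2022-04-10. Table 2 makes the start 2022-03-01, so the rule gives prior only, although use after the first dose is certain.

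**3. Size.** The only input from the documents is N = 600. All rates below are assumed.

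*Patients misplaced.* Let q be the share on a continuing medicine and r the share starting a new one, independent of each other. Yes by the rule = 600r. Yes by the definition = 600[1 − (1−q)(1−r)]. Coded No while co-medicated = 600q(1−r). For q from 0.3 to 0.9 and r from 0.1 to 0.3 these give 60–180, 222–558 and 126–486 patients.

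*Table B7.* With q = 0.8 and r = 0.3 the rule reports 30%. True use is 1 − 0.2×0.7 = 86% under independence, with bounds max(0.8, 0.3) = 80% and min(1, 1.1) = 100%.

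*AE factor, no true effect.* AE risk 0.2, ongoing share p = 0.8, share of AEs treated with a new drug t = 0.5, other new starts n = 0.2, all independent.
- Rule: P(Yes | AE) = 1 − 0.5×0.8 = 0.60; P(Yes | no AE) = 0.20; odds ratio = (0.60/0.40)/(0.20/0.80) = 6.0.
- Definition: P(Yes | AE) = 1 − 0.2×0.5×0.8 = 0.92; P(Yes | no AE) = 1 − 0.2×0.8 = 0.84; odds ratio = (0.92/0.08)/(0.84/0.16) = 2.19.
- With t from 0.3 to 0.7 and n of 0.2 or 0.3: 2.4–12.7 by the rule, against 1.5–3.8 by the definition at p = 0.8 (1.5–4.9 for p from 0.5 to 0.9).
- No group under the definition: 1 − (0.2×0.92 + 0.8×0.84) = 0.144, about 86 of 600.
- Restricted to medicines in use at the first dose, the odds ratio is 1.0 in this null case.

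*AE factor, true effect.* Suppose any medicine in use doubles AE risk and no drug is given for an AE. If a share p of the No group takes an ongoing medicine, the observed risk ratio is 2/(1+p): 1.43 at p = 0.4 and 1.11 at p = 0.8.

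**The case against.** The strongest reply is that the rule and all nine examples agree, so the plan yields one reproducible classification into two exclusive groups, and no record is lost because continuing medicines appear in Table B6. The prior-medication factor sits directly above the concomitant one in every list, so patients on long-term medicines are visible as Yes there. On this view the defect is one sentence and a label. This does not repair the problem: Prior also holds medicines stopped before the first dose (row 1), so neither B6 nor the prior factor shows co-use, and the concomitant factor stays mislabelled.

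Several points do stand:
- The analyses are descriptive and this is one of many univariate factors. As worded, entry to the multivariable models follows simple logistic regression, which is specified for continuous variables, so the flag does not clearly reach them.
- In the null illustration the 6.0 does not depend on the ongoing share; it comes from AE-treating drugs. The AE risk in the No group is 11.1% under both readings (0.08/0.72 and 0.016/0.144) against a true 20%. The corrected definition lowers the Yes-group risk from 0.12/0.28 = 43% to 0.184/0.856 = 21%, but does not remove that bias.
- A sensitivity analysis on medicines in use at the first dose would partly overlap the prior factor, since baseline recording covers the preceding month.

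**Conclusion.** The concern holds. SAP 7.3.5 contradicts itself: the start-date rule and rows 2 to 4 of Table 5 deny the concomitant label to medicines that its own definition includes. The protocol's recording sections use the broad meaning, and no change is declared. Misclassification is certain for any patient whose only co-medication continues from before the first dose.

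How many patients this affects, and which way it moves the factor tests, cannot be settled from the documents. Of the illustrated null odds ratio of 6.0, only the gap down to 2.2 belongs to this rule; the remainder is AE-treating drugs, which count as Yes under either reading. The dilution example runs the other way. No size is claimed for the HbA1c or final-effectiveness comparisons. It should be fixed, because the affected tables would be misread, but the headline safety and effectiveness results do not depend on it.

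**What to change.** In SAP 7.3.5, class a medicine as concomitant if it is ongoing or its end date is on or after the first Esgliteo dose, whatever its start date. Let a medicine be both prior and concomitant, mark rows 2 to 4 of Table 5 in both columns, and footnote that B6 and B7 overlap. Produce B7, C16, D5, D7 and D15 on the corrected flag, together with the medication line in the disease-information table (B2, SAP 7.3.2). A medicine with an imputed start day may still be flagged prior when it began after the first dose, but its concomitant status will be right.

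Separately, because drugs started for an AE remain Yes, add one sensitivity version of the AE factor test using medicines in use at the first dose, labelled as such. It ignores medicines started later. The corrected No group may also be small (about 86 of 600 under the assumptions above), so the main test will be imprecise.

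If exclusive categories are really intended, the minimum repair is to rename the second one as newly started medication wherever it appears. That would leave co-use untabulated.

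The cost is SAP wording, three table rows, one derivation from start and end dates that Table 2 already handles, and one extra table. No new data are needed. If the SAP is not reissued, its introduction already provides for recording the change and the reason in the final report.
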